6.2 Eligibility criteria in China

6.2.1 Inclusion criteria

To be eligible to participate in this study, all of the following criteria must be met for subjects in China:

1. An Institutional Review Board (IRB)/Independent Ethics Committee (IEC) approved written informed consent signed and dated by the subject or by parent(s) or legally representative. The consent form or a specific assent form, where required, will be signed and dated by minors.
2. Male/female subject from 16 years of age or older. Subjects who are not legal adults may only be included where legally permitted and ethically accepted.
3. Subject completed the Treatment Period and Transition Period of EP0083.
4. Subject for whom the Investigator believes a reasonable benefit from the long-term administration of BRV may be expected.
5. Female subjects without childbearing potential (postmenopausal for at least 2 years, bilateral oophorectomy or tubal ligation, complete hysterectomy) are eligible. Female subjects with childbearing potential are eligible if they use a medically accepted contraceptive method. Oral or depot contraceptive treatment with at least approved dosage of ethinylestradiol per intake in each country where this study is conducted (if subjects is taking any enzyme inducer such as carbamazepine, phenobarbital, primidone, phenytoin, oxcarbazepine, St.

John's Wort or rifampicin, the dosage of ethinylestradiol should have been modified according to the guidelines for contraceptive treatment in each country), monogamous relationship with vasectomized partner, or barrier contraception are acceptable methods. The subject must understand the consequences and potential risks of inadequately protected sexual activity, be educated about and understand the proper use of contraceptive methods, and undertake to inform the Investigator of any potential change in status. Abstinence will be considered as an acceptable method of contraception if the Investigator can document that the subject agrees to be compliant.

6. Subject/legally representative considered as reliable and capable of adhering to the protocol (eg, able to understand and complete diaries and questionnaires), visit schedule, or medication intake according to the judgment of the Investigator.

6.2.2 Exclusion criteria

Subjects in China are not permitted to enroll in the study if any of the following criteria is met:

1. Subject has developed hypersensitivity to any components of the IMP or comparative drugs as stated in this protocol during the course of the core study.
2. Severe medical, neurological or psychiatric disorders, or laboratory values which may have an impact on the safety of the subject.
3. Poor compliance with the visit schedule or medication intake in the previous BRV studies.
4. Planned participation in any other clinical study of another investigational drug or device during this study.
5. Pregnant or lactating woman.
6. Any medical condition which, in the Investigator's opinion, warrants exclusion.
7. Subject has a lifetime history of suicide attempt (including an active attempt, interrupted attempt, or aborted attempt), or has suicidal ideation in the past 6 months as indicated by a positive response ("Yes") to either Question 4 or Question 5 of the Columbia-Suicide Severity Rating Scale (C-SSRS) at the EV.
8. Subject has $>2 \times$ upper limit of normal (ULN) of any of the following at the EV: alanine aminotransferase (ALT), aspartate aminotransferase (AST), alkaline phosphatase (ALP), or $>\text{ULN}$ total bilirubin ($\geq 1.5 \times \text{ULN}$ total bilirubin if known Gilbert's syndrome).

If subject has elevations only in total bilirubin that are $>\text{ULN}$ and $<1.5 \times \text{ULN}$, fractionate bilirubin to identify possible undiagnosed Gilbert's syndrome (ie, direct bilirubin $<35\%$).

6.3 Withdrawal criteria

Subjects are free to withdraw from the study at any time, without prejudice to their continued care.

Subjects should be withdrawn from the study if any of the following events occur:

- Withdrawal for safety reasons by the Investigator such as a worsening of the seizure profile, eg, occurrence of status epilepticus, seizure clustering or generalized tonic-clonic seizure, if unknown for the subject

- Subject develops an illness that would interfere with his/her continued participation.
- Subject is noncompliant with the study procedures or medications in the opinion of the Investigator.
- Subject takes prohibited concomitant medications as defined in this protocol.
- Subject or legal guardian withdraws his/her consent.
- There is confirmation of a pregnancy during the study, as evidenced by a positive pregnancy test.
- The sponsor or a regulatory agency requests withdrawal of the subject.
- In the event of a suicide attempt, the subject should be referred immediately to a Mental Healthcare Professional and must be withdrawn from the study.

Subject has active suicidal ideation without specific plan as indicated by a positive response (“Yes”) to Question 4 of the “Since Last Visit” version of the C-SSRS. The subject should be referred immediately to a Mental Healthcare Professional and may be withdrawn from the study based upon the Investigator’s judgment of benefit/risk of continuing the subject in the study/on study medication.

Subject has active suicidal ideation with a specific plan as indicated by a positive response (“Yes”) to Question 5 of the “Since Last Visit” version of the C-SSRS. The subject should be referred immediately to a Mental Healthcare Professional and must be withdrawn from the study.

Investigators should attempt to obtain information on subjects, in the case of withdrawal or discontinuation. The Investigator should make effort (at least 1 phone call and 1 written message to the subject) and document his/her effort (date and summary of the phone call and copy of the written message in the source documents), to complete the final evaluation. All results of these evaluations and observations, together with a narrative description of the reason(s) for removing the subject, must be recorded in the source documents. The eCRF must document the primary reason for withdrawal or discontinuation.

Investigators should contact the Medical Monitor, whenever possible, to discuss the withdrawal of a subject in advance.

6.3.1 Potential drug-induced liver injury IMP discontinuation criteria

Subjects with potential drug-induced liver injury (PDILI) must be assessed to determine if IMP must be discontinued. In addition, all concomitant medications and herbal supplements that are not medically necessary should also be discontinued.

The PDILI criteria below require immediate and permanent discontinuation of IMP:

- Subjects with either of the following:
 - ALT or AST $\geq 5 \times \text{ULN}$
 - ALT or AST $\geq 3 \times \text{ULN}$ and coexisting total bilirubin $\geq 2 \times \text{ULN}$

The PDILI criterion below requires immediate discontinuation of IMP:

- Subjects with ALT or AST $\geq 3 \times \text{ULN}$ who exhibit temporally associated symptoms of hepatitis or hypersensitivity. Hepatitis symptoms include fatigue, nausea, vomiting, right upper quadrant pain or tenderness. Hypersensitivity symptoms include fever (without clear alternative cause), rash, or eosinophilia (ie, $>5\%$).

The PDILI criterion below allows for subjects to continue on IMP at the discretion of the Investigator.

- Subjects with ALT or AST $\geq 3 \times \text{ULN}$ (and $\geq 2 \times \text{Baseline}$) and $< 5 \times \text{ULN}$, total bilirubin $< 2 \times \text{ULN}$, and no eosinophilia (ie, $\leq 5\%$), with no fever, rash, or symptoms of hepatitis (eg, fatigue, nausea, vomiting, right upper quadrant pain or tenderness).

Evaluation of PDILI must be initiated as described in [Section 10.2.1](#). If subjects are unable to comply with the applicable monitoring schedule, IMP must be discontinued immediately.

Investigators should attempt to obtain information on subjects in the case of IMP discontinuation to complete the final evaluation. Subjects with PDILI should not be withdrawn from the study until investigation and monitoring are complete. All results of these evaluations and observations, as well as the reason(s) for IMP discontinuation and subject withdrawal (if applicable), must be recorded in the source documents. The eCRF must document the primary reason for IMP discontinuation.

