Laboratory value		Symptoms ^a of hepatitis or hypersensitivity	Immediate		Follow up	
ALT or AST	Total bilirubin		Consultation requirements	Actions	Testing	Evaluation
≥3xULN	≥2xULN ^b	NA	Hepatology consult. ^c Medical Monitor must be notified within 24 hours (eg, by laboratory alert) and subject discussed with Medical Monitor ASAP.	Immediate, permanent IMP discontinuation.	Essential: Must have repeat liver chemistry values and additional testing completed ASAP (see Section 10.2.1.3); recommended to occur at the site with HCP.	Monitoring of liver chemistry values at least twice per week until values normalize, stabilize, or return to within baseline values. ^d
≥3xULN	NA			Immediate, temporary or permanent, IMP discontinuation.		
≥5xULN (and ≥2x Baseline)	<2xULN	No	Discussion with Medical Monitor required. Hepatology consult required if ALT/AST ≥8xULN	Immediate IMP discontinuation	Essential: Every attempt must be made to have repeat liver chemistry values and additional testing completed within 48 hours at the site with HCP (see Section 10.2.1.3).	

Table 10–2: Required investigations and follow up for PDILI

Laboratory value		Symptoms ^a of hepatitis or hypersensitivity	Immediate		Follow up	
ALT or AST	Total bilirubin		Consultation requirements	Actions	Testing	Evaluation
≥3xULN (and ≥2x Baseline) and <5xULN	<2xULN	No	Discussion with Medical Monitor required if the criterion that allows for IMP continuation is met.	Further investigation – immediate IMP discontinuation not required (see Section 10.2.1.2). IMP discontinuation required if any of the following occur: Subject cannot comply with monitoring schedule. Liver chemistry values continue to increase. Liver chemistry values remain ≥3xULN (and ≥2xBaseline) after 2 week monitoring without stabilization or evidence of resolution.	Not required unless otherwise medically indicated (at discretion of Investigator)	Monitoring of liver chemistry values at least twice per week for 2 weeks ^d Immediate IMP discontinuation required if: Liver chemistry values continue to increase. After 2 weeks of monitoring liver chemistry values: Liver chemistry values remain ≥3xULN (and ≥2x Baseline) after 2 weeks of monitoring without stabilization or evidence of resolution Continue to monitor until values normalize, stabilize, or return to within Baseline values ^d

Table 10–2: Required investigations and follow up for PDILI

Laboratory value		Symptoms ^a of hepatitis or hypersensitivity	Immediate		Follow up	

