10.2.1.2 Immediate action: determination of IMP discontinuation

All PDILI events require immediate action, testing, and monitoring.

The immediate action is dependent on the laboratory values and symptoms of hepatitis or hypersensitivity and ranges from continuation of IMP (followed by immediate investigation) to immediate and permanent discontinuation (see [Section 6.3.1](#) and [Table 10-2](#) for details).

When IMP is discontinued, all concomitant medications and herbal supplements that are not medically necessary should also be discontinued. The Investigator should also consider dose reduction for medically necessary concomitant medication and consider changing any medically required concomitant medication known to be hepatotoxic to a suitable alternative.

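### At ALT or AST ≥5xULN, Protocol Section 6.3.1 and Table 10-2 give different stopping actions: a direct conflict for symptomatic subjects with bilirubin <2xULN, and an unstated permanence for asymptomatic ones

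*Protocol*

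**What the plan says.** Protocol Section 6.3.1 has three tiers.

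- The first opens with "The PDILI criteria below require immediate and permanent discontinuation of IMP". It lists ALT or AST ≥5xULN on its own, and ALT or AST ≥3xULN together with total bilirubin ≥2xULN.
- The second opens with "The PDILI criterion below requires immediate discontinuation of IMP". It covers ALT or AST ≥3xULN with symptoms of hepatitis or hypersensitivity and does not mention permanence.
- The third lets the investigator continue treatment for asymptomatic values from 3 to below 5xULN (and at least twice Baseline) with bilirubin <2xULN.

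Table 10-2, in Section 10.2.1, has its own column of actions.

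- ≥3xULN with bilirubin ≥2xULN: "Immediate, permanent IMP discontinuation".
- ≥3xULN with bilirubin marked not applicable and no upper limit on ALT/AST: "Immediate, temporary or permanent, IMP discontinuation".
- "≥5xULN (and ≥2x Baseline"), with bilirubin <2xULN and symptoms No: "Immediate IMP discontinuation".
- From 3 to below 5xULN, bilirubin <2xULN, no symptoms: further investigation, with no immediate stop required.

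The opening of Section 10.2.1 names Section 6.3.1 as the place where the discontinuation criteria stand. Section 10.2.1.2 says "The immediate action is dependent on the laboratory values and symptoms of hepatitis or hypersensitivity" and refers the reader to both Section 6.3.1 and Table 10-2 for the details.

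**The concern.** This is a safety stopping rule in a study whose primary objective is long-term safety and tolerability. The protocol states the rule twice, and at ALT or AST ≥5xULN the two statements do not match. An investigator working from the table could regard a temporary stop as compliant in a subject for whom Section 6.3.1 requires a permanent one. Neither Section 6.3.1 nor Section 10.2.1 describes how or when treatment would resume, so a temporary stop has no defined next step.

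The action taken also determines where a case is reported. SAP Section 9.2.2.2 tabulates events whose recorded action is permanent withdrawal. Section 9.2.2.7 tabulates dose changes and temporary interruptions. Section 5.4 counts BRV discontinuation as the Kaplan-Meier event. Section 9.1.1 does not subtract treatment gaps from exposure.

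**Working it through.** No planned figure depends on this rule, so the check sets the two texts side by side for each combination. ALT/AST and bilirubin are in multiples of ULN.

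| ALT/AST | Bilirubin | Symptoms | ≥2x Baseline | Section 6.3.1 | Table 10-2 | Result |
|---|---|---|---|---|---|---|
| ≥5 | <2 | Yes | either | immediate, permanent | immediate, temporary or permanent | direct conflict |
| ≥5 | <2 | No | Yes | immediate, permanent | immediate, permanence unstated | omission |
| ≥5 | <2 | No | No | immediate, permanent | no row applies | gap, if it can arise |
| ≥5 | ≥2 | No | either | immediate, permanent | immediate, permanent | agree |
| ≥5 | ≥2 | Yes | either | immediate, permanent | permanent row applies; temporary-or-permanent row also matches | agree on the first row; rows overlap |
| 3 to <5 | ≥2 | No | either | immediate, permanent | immediate, permanent | agree |
| 3 to <5 | ≥2 | Yes | either | immediate, permanent | same two rows overlap | as above |
| 3 to <5 | <2 | Yes | either | immediate, permanence unstated | immediate, temporary or permanent | compatible |
| 3 to <5 | <2 | No | Yes | may continue | may continue | agree |

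**Worked case.** Take ALT 6xULN, bilirubin 1xULN and hepatitis symptoms. Under Section 6.3.1, 6 ≥ 5, so the stop is immediate and permanent. The subject also meets the second tier (≥3xULN with symptoms), but that does not cancel the unconditional ≥5xULN criterion. In Table 10-2 the ≥5xULN row requires no symptoms and does not fit. The ≥3xULN row fits and allows a temporary stop.

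**The blank cell.** The symptoms cell of that ≥3xULN row is empty in the text as read from the PDF. I take it as Yes, because the matching criterion in Section 6.3.1 is ≥3xULN with symptoms. This is the narrower reading: with no symptom restriction, the row would also cover asymptomatic subjects at ≥5xULN and the conflict would widen.

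**The Baseline condition.** For a value of x times ULN, the condition fails only when Baseline exceeds x/2.

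- At the threshold, x = 5, so Baseline would have to exceed 5/2 = 2.5xULN.
- The exclusion criteria in Sections 6.1.5, 6.1.6 and 6.2.2 bar subjects above 2xULN at the Entry Visit (rollover subjects) or Screening Visit (direct enrollers).
- If Baseline is that capped value, the ratio at the threshold is at least 5/2 = 2.5, which is above 2. The condition is then always met and the gap in the third line of the table cannot arise.
- The protocol does not say which value is Baseline for PDILI. SAP Sections 3.3 and 9.3 take baseline for rollover subjects from the core study (EP0083 or N01358). The liver entry limits of those studies are not in the documents, so the capped-value reading is an assumption.

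**The case against.** The strongest reply is that the protocol already sets a precedence. Section 10.2.1 opens by placing the discontinuation criteria in Section 6.3.1, and the table's title presents it as a guide to investigation and follow-up. On that view the table is secondary, and its silence on permanence in the ≥5xULN row is filled in by Section 6.3.1. For the asymptomatic subject much of this stands: an omission is not a contradiction. For the symptomatic subject it does not settle the matter. The table has its own action column, that column expressly permits a temporary stop, and Section 10.2.1.2 cites both texts for the action without ranking them.

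A second reply is that temporary or permanent includes permanent, so a site that stops permanently satisfies both texts. That is true. In addition, Section 10.2.1.1 requires the Medical Monitor to be notified within 24 hours and the case discussed, which makes an unreviewed restart less likely. Neither point removes the divergent instruction.

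Two stronger readings are tempting. A reader might infer that the table lets every subject at ≥5xULN with bilirubin <2xULN be stopped only temporarily. The documents do not support that: the table's own ≥5xULN row does not mention a temporary stop, and no row limits the stop to a temporary one. A reader might also infer that the inconsistency directly distorts the safety outputs. It does not: SAP Sections 9.2.2.2 and 9.2.2.7 report the action recorded, and Section 5.4 uses actual dosing dates and recorded discontinuation. No derivation applies the PDILI rule.

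**Conclusion.** The inconsistency is real and lies in the current text, but it is narrow. The direct conflict concerns subjects with ALT or AST ≥5xULN, bilirubin <2xULN and symptoms, on the stated reading of the blank cell. For asymptomatic subjects with the same laboratory values, the table omits permanence and adds a Baseline condition. That condition has no practical effect only if Baseline is the entry or screening value limited to 2xULN. Where bilirubin is ≥2xULN and there are no symptoms, the two texts agree.

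The number of subjects affected cannot be estimated from the documents and may be small. The effect on the TEAE and time-to-discontinuation tables is indirect, through what sites actually do. The point still merits correction, because it concerns a stopping rule that two sites could apply differently while each follows the protocol. Nothing here implies that either text is the clinically correct one.

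**What to change.** Reconcile Section 6.3.1 and Table 10-2 so that each combination of ALT/AST, bilirubin and symptoms leads to one action, worded identically in both places. State for every row whether the discontinuation is permanent. Fill in or confirm the symptoms entry of the ≥3xULN row, and say which row applies when a subject matches two. Either carry the Baseline condition in both texts or in neither, and define which value is Baseline for PDILI. The sponsor's medical team should decide which text is correct.

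The cost is a wording change in the next protocol amendment and a notice to sites. No analysis needs to change.

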7 STUDY TREATMENTS

7.1 Description of investigational medicinal products

Oral film-coated tablets of BRV 25mg and BRV 50mg will be used in this study.

7.2 Treatments to be administered

Directly enrolled subjects in Japan and subjects rolling over from EP0083 will be started on a BRV dose of 100mg/day (2 equally divided doses administered twice daily) at study entry and should be maintained at this dose for at least 2 weeks, unless the subject is not able to tolerate treatment.

Subjects from Japan who entered from N01379 can enter EP0085 at a dose up to 200mg/day. The BRV dose can be adjusted based on the individual subject's seizure control and tolerability between 50mg/day and 200mg/day during the study and must always be administered in equal morning and evening doses except the last week of down-titration. Of note, decreasing the dose should not exceed 50mg/day.

For all subjects, the first intake of study medication should occur in the evening of the day of the EV. Subjects should take tablets according to instructions provided by the Investigator.

During the Down-Titration Period, the BRV dose may be decreased in steps of a maximum of 50mg/day on a weekly basis. A last down-titration step at 25mg/day for 1 week should be included prior to the 2-week Study Drug-Free Period. The subject will be required to enter a 2-week Study Drug-Free Period for 2 weeks, followed by a FV.

7.3 Packaging

Brivaracetam tablets are manufactured, packaged, and labeled according to Good Manufacturing Practice guidelines and applicable laws or regulations. The IMP is suitably packaged in such a way as to protect the IMP from deterioration during transport and storage.

7.4 Labeling

Clinical drug supplies will be labeled in accordance with the current International Council for Harmonisation (ICH) guidelines on Good Clinical Practice (GCP) and Good Manufacturing Practice and will include any locally required statements. If necessary, labels will be translated into the local language.

7.5 Handling and storage requirements

The Investigator (or designee) is responsible for the safe and proper storage of IMP at the site. Investigational medicinal product stored by the Investigator (or designee) is to be kept in a secured area with limited access according to the storage conditions mentioned on the label.

Appropriate storage conditions must be ensured either by controlling the temperature (eg, room, refrigeration unit) or by completion of a temperature log in accordance with local requirements on a regular basis (eg, once a week), showing actual and minimum/maximum temperatures reached over the time interval.

In case an out-of-range temperature is noted, it must be immediately reported as per instructions contained in the IMP Handling Manual.

The Investigator (or designee) will instruct the subject to store the IMP following the instructions on the label.

7.6 Drug accountability

A Drug Accountability form will be used to record IMP dispensing and return information on a by-subject basis and will serve as source documentation during the course of the study. Details of any IMP lost, damaged (due to breakage or wastage), not used, partially used, disposed of at the study site, or returned to the sponsor or designee must also be recorded on the appropriate forms. All supplies and pharmacy documentation must be made available throughout the study for UCB (or designee) to review.

Periodically, and/or after completion of the clinical phase of the study, all used (including empty containers)/partially used, unused, damaged, and/or expired IMP must be reconciled and returned to UCB (or designee) preferably in the original package. Investigational medicinal product intended for the study cannot be used for any other purpose than that described in this protocol.

7.7 Procedures for monitoring subject compliance

The IMP will be supplied to the subject/parent(s)/legal representative(s) at protocol specified time points provided in [Table 5-1](#) and [Table 5-2](#)).

The Investigator will instruct the subject/parent(s)/legal representative(s) to bring back at each visit the kits (even empty) dispensed at the previous visit and containing all the remaining tablets of study medication.

The subject/parent(s)/legal representative(s) must record the situation of medication compliance every time the subject takes an IMP.

Drug accountability must be done in the subject/parent(s)/legal representative(s) presence in order to obtain explanations regarding discrepancies in compliance with the dosing regimen. Drug accountability must be recorded on the Drug Accountability form.

Compliance with investigational product is defined as investigational product consumption by the subject within 80% and 120% of the prescribed dosage. If a subject is found to be persistently noncompliant (<80% or >120%), the Sponsor in conjunction with the Investigator will make a decision as to whether the subject should be withdrawn from the study.

The number of tablets dispensed and returned must be recorded in the source documents.

